2.1.2 Prior or concomitant medications

Concomitant medications are defined as all medications other than study drug administered to a patient from the study enrollment until the end of the study.

Local standard treatment of hemophilia, which is considered to be, but not limited to, IV infusion of FVIII or FIX concentrates, aPCC or rFVIIa are used for Factor/BPA Prophylaxis and bleeding episode management. Use of these agents will be captured in the patient's eDiary.

Other concomitant medications including all prescription medications, herbal preparations, over the counter medications, vitamins, and minerals are to be reported in the case report form (CRF) pages.

Prior medications for HCV treatment before study enrollment are also collected at screening visit.

Any technical details related to computation, dates, imputation for missing dates are described in [Section 2.5](#).

2.1.3 Efficacy endpoints

2.1.3.1 Primary efficacy endpoint

Global protocol: The primary efficacy endpoint of the study is annualized bleeding rate (ABR) in the fitusiran efficacy period and the factor/BPA prophylaxis period.

US protocol: The primary efficacy endpoint of the study is annualized bleeding rate (ABR) in the fitusiran treatment period and the BPA prophylaxis period.

Bleeding Episode Definitions

The primary source of bleeding data is the eDiary. Additional bleeding data may be captured from the bleeding diary pages of the CRF, if not reported in the eDiary. Any other sources of bleeding data will be discussed in the CSR.

A bleeding episode is defined as any occurrence of hemorrhage that may require administration of factor or BPA infusion, eg, hemarthrosis, muscle, or mucosal bleeding episodes.

The start time of a bleeding episode will be considered the time at which symptoms of bleeding episode first develop. Bleeding or any symptoms of bleeding at the same location that occurs within 72 hours of the last injection used to treat a bleed or 72 hours after the start of an untreated bleed at that location will be considered a part of the original bleeding event, and will count as one bleeding episode towards the ABR. Any bleeding symptoms that begin more than 72 hours from the last injection used to treat a bleed or 72 hours after the start of an untreated bleed at that location will constitute a new bleeding event.

A spontaneous bleeding episode is a bleeding event that occurs for no apparent or known reason, particularly into the joints, muscles, and soft tissues.

Bleeding episodes sustained during sports and recreation will be counted as traumatic bleeding episodes.

Traumatic bleeds that occur in different locations simultaneously (same date/time) in the same patient will be considered as one bleeding episode. Spontaneous bleeds that occur simultaneously (same date/time) in different locations in the same patient will be considered as separate bleeds.

A joint bleeding episode is characterized by an unusual sensation in the joint (“aura”) in combination with 1) increasing swelling or warmth over the skin over the joint, 2) increasing pain or 3) progressive loss of range of motion or difficulty in using the limb as compared with baseline.

A target joint is defined as a joint where 3 or more spontaneous bleeding episodes in a single joint within a consecutive 6-month period has occurred; where there has been ≤ 2 bleeding episodes in the joint within a consecutive 12-month period the joint is no longer considered a target joint.

Efficacy analysis will focus on observed data as collected, unless otherwise specified. Patients who discontinue study drug during the study will be strongly encouraged to continue study participation including the recording of bleeding episode data. Only bleeding episodes that are treated with BPA/factor will be included in the primary analysis of endpoints evaluating bleeding.

Annualized bleeding rate will be calculated as described in [Section 2.4.4.1.1](#).

Efficacy Period and factor/BPA prophylaxis Period

In the protocol, for the purpose of ABR calculation, the factor/BPA prophylaxis period and fitusiran “Onset Period”, “Efficacy Period” and “Treatment Period” are defined. The factor/BPA prophylaxis period is defined as the 6 months period before the first dose of fitusiran, during which patients continue their pre-study, regularly scheduled prophylaxis regimen with factor concentrates or BPAs. The Onset Period is defined as the first 28 days after the first dose of fitusiran, during which the AT lowering capacity of fitusiran is increasing but has not yet reached therapeutic levels. The Efficacy Period is defined as starting on Day 29 when the AT lowering capacity of fitusiran has achieved therapeutic target range. The Treatment Period is defined as the onset period plus the efficacy period. The window for each period is summarized in the table below.

Period	Definition
Factor/BPA prophylaxis period	Day -168 to the earlier of Day -1 or the last day of bleeding follow up
Fitusiran onset period	Day 1 to the earlier of Day 28 or the last day of bleeding follow up
Fitusiran efficacy period	Day 29 to the earlier of Day 190 or the last day of bleeding follow up
Fitusiran treatment period	Onset period plus the efficacy period

The last day of bleeding follow up is defined as the deactivation date captured in eDiary.

If a patient does not have bleeding episode data collected after Day 28 due to early study discontinuation in the fitusiran treatment period, the efficacy period will be from Day 1 to the earlier of date of study discontinuation and the last day of bleeding follow up.

The factor/BPA prophylaxis period, fitusiran onset period, efficacy period and treatment period also exclude the period of following intercurrent events to avoid confounding of treatment effect for the primary efficacy analysis based on On-Treatment Strategy.

- Permanent fitusiran treatment discontinuation during treatment period: Exclude events occurring on any dates starting from the date of the last dose within treatment period +29 days. For patients whose last dose is on 50 mg/20 mg Q2M regimen, the “29 days” adjustment will be replaced with 57 days.
- Perioperative period of major surgery. The perioperative period is defined as the day of the surgery through the final day on which supplemental hemostatic or antithrombotic treatments are administered as part of the perioperative treatment plan.
- Period of minor surgery is defined as the perioperative period of surgery above or to 72 hours from the end of surgery, whichever is later.
- Period of antithrombin treatment is defined as the first day of antithrombin treatment through the final day on which antithrombin or other anticoagulant therapies are administered plus 5 half-lives of that specific product.
- After prophylactic treatment with emicizumab.

The summary statistics for number of patients who are lost-to-follow-up and who had each intercurrent event will be provided.

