11.2 PERIOPERATIVE SCHEDULE OF ASSESSMENTS

11.2.1 Definitions of minor and major surgery

Minor surgery is defined as any invasive operative procedure in which only skin, mucous membranes, or superficial connective tissue is manipulated and does not meet the criteria for major surgery (eg, dental extraction of <3 non-molar teeth). Minor surgical procedures may be performed at a local health care provider institution.

Major surgery is defined as any invasive operative procedure that requires any of the following:

- Opening into a major body cavity (eg, abdomen, thorax, skull)
- Operation on a joint
- Removal of an organ
- Dental extraction of any molar teeth or ≥ 3 non-molar teeth
- Operative alteration of normal anatomy
- Crossing of a mesenchymal barrier (eg, pleura, peritoneum, dura)

It is strongly recommended that any elective non-dental major surgery be performed at a clinical study center, when possible.

11.2.2 Perioperative assessments of safety and hemostatic efficacy in patients undergoing major operative procedures

In patients undergoing major operative procedures during the fitusiran treatment period, safety and hemostatic efficacy assessments will be performed according to the Perioperative Schedule of Assessments (described below and outlined in [Table 12](#), where possible).

After a review of medical and surgery history has been completed, patients will have the following assessed as specified in the Perioperative Schedule of Assessments ([Table 12](#)): directed physical examination and assessment of vital sign measurements; clinical laboratory assessments including hematology (complete blood count, white blood count, red blood cell count, hemoglobin, hematocrit, platelets); coagulation (APTT, PT/INR, fibrinogen, D-dimer); hepatic assessments; and hemostatic efficacy assessments (rating scale based on ISTH Scientific and Standardization Committee [SSC] definitions) ([18](#)).

Table 12 - Perioperative schedule of assessments in patients undergoing major operative procedures

| | Perioperative Evaluation Period ^a | | | | |
|--|--|---------------------------------|-----------------------|---------------------------|-----------------------|
| | Preoperative Screening | Dental/Surgical Procedure Visit | Postoperative Visit 1 | Postoperative Visit 2 | Postoperative Visit 3 |
| | SDay -3 to SDay -1 | SDay 0 | SDay 1 ^b | SDay 2 to 14 ^c | SDay 28 ^d |
| Directed Physical Examination ^d | X | | | | X |

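### The on-treatment rule gives minor surgery a 72-hour minimum exclusion but major surgery none, so a major procedure whose cover ends before about surgery day 3 is excluded for 1 to 3 fewer days

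*SAP*

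**What the plan says.** SAP 2.1.3.1 lists the intercurrent events removed from the on-treatment analysis: "The factor/BPA prophylaxis period, fitusiran onset period, efficacy period and treatment period also exclude the period of following intercurrent events". Two consecutive bullets deal with surgery.

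- For a major procedure: "Perioperative period of major surgery. The perioperative period is defined as the day of the surgery through the final day on which supplemental hemostatic". The sentence goes on to include antithrombotic treatment and ties both to the perioperative plan. No minimum is given.
- For a minor procedure: "Period of minor surgery is defined as the perioperative period of surgery above or to 72 hours from the end of surgery, whichever is later".

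Other relevant text:

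- Protocol 6.6 defines the perioperative evaluation period in the same way, also without a minimum.
- Protocol 11.2.1 counts "Dental extraction of any molar teeth" as major surgery. Extraction of fewer than three non-molar teeth is its example of minor surgery.
- SAP 2.1.3.1 limits the count to treated bleeds: "Only bleeding episodes that are treated with BPA/factor will be included in the primary analysis of endpoints evaluating bleeding".
- Protocol 8.2.5.1 drops bleed data during and after major surgery, with no stated end, and does not mention minor surgery. SAP Table 4 declares that the exclusion periods are redefined in SAP 2.1.3.1, so the SAP bullets are the operative rule.
- SAP 2.4.4.1.2 (treatment policy) leaves out events due to major or minor surgery. That is a rule of attribution, not a window of days.

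**The concern.** The exclusions exist to keep bleeds caused by surgery from confounding the treatment comparison. That reason applies at least as strongly to a major procedure as to a minor one. As drafted, the minor window can never be shorter than the major window, and it is longer whenever supplemental cover stops early. The SAP gives no reason for this ordering.

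Elsewhere the SAP accepts that effects outlast treatment. The antithrombin exclusion runs on for five half-lives, and joint scores are set aside until 7 days after the perioperative period (SAP 2.4.7.5).

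At stake is whether some surgical bleeds enter the primary ABR. The same bleed could be counted in the primary on-treatment analysis, which is meant to remove confounding, and left out of the supportive treatment-policy analysis as due to surgery.

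**Working it through.** **1. Length of the two windows.** Let cover end on surgery day k (SDay k, with the day of surgery as 0), and take 72 hours from the end of surgery as reaching SDay 3. The documents give no cover lengths, so k is varied.

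- Major: k + 1 calendar days.
- Minor: max(k, 3) + 1 calendar days.

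| Cover ends on | Major | Minor | Gap |
|---|---|---|---|
| SDay 0 | 1 | 4 | 3 |
| SDay 1 | 2 | 4 | 2 |
| SDay 2 | 3 | 4 | 1 |
| SDay 3 | 4 | 4 | 0 |
| SDay 4 | 5 | 5 | 0 |

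The gap exists only when cover ends before SDay 3.

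**2. Does another rule close the gap?**

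- The 72-hour merging rule in SAP 2.1.3.1 runs from an injection used to treat a bleed, or from the start of an untreated bleed. It does not run from surgical cover.
- The antithrombin exclusion helps only if antithrombin is given.
- If treatment of the post-operative bleed is itself part of the perioperative plan, the major window extends and the bleed drops out. The SAP does not say whether it is.

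Illustration: molar extraction on Day 100, one dose of cover that day, a socket bleed treated on Day 102. Under the major rule only Day 100 is excluded and the bleed counts. Under the minor rule Days 100 to 103 are excluded and it does not. This holds only if the Day 102 treatment lies outside the perioperative plan.

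**3. One patient.** The efficacy period is "Day 29 to the earlier of Day 190 or the last day of bleeding follow up", so at most 190 − 29 + 1 = 162 days. One counted bleed in an otherwise bleed-free patient gives an ABR of 365.25/(162 − (k + 1)):

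- k = 0: 365.25/161 = 2.27
- k = 1: 365.25/160 = 2.28
- k = 2: 365.25/159 = 2.30

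**4. One cohort.** At the planning fitusiran ABR of 4 (SAP 1.3), expected bleeds are N × 4 × 162/365.25. The proportional rise for m extra bleeds is m divided by that count. The number of such bleeds is not documented, so one and three are shown; zero is also plausible.

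| N | Expected bleeds | One extra | Three extra |
|---|---|---|---|
| 30 (Cohort A) | 53.2 | +1.9% | +5.6% |
| 40 (Cohort B as simulated) | 71.0 | +1.4% | +4.2% |
| 50 (Cohort B as planned) | 88.7 | +1.1% | +3.4% |

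**5. The other period.** The rule also applies in the prophylaxis period, which the SAP sets at up to 168 days (Day -168 to Day -1). A bleed counted there lowers the ratio. For Cohort B at ABR 4 and N=50 the expected count is 50 × 4 × 168/365.25 = 92.0, so one extra bleed lowers the ratio by about 1.1%. For Cohort A at ABR 16 and N=30 it is 30 × 16 × 168/365.25 = 220.8, a fall of about 0.5%.

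**The case against.** The best defence is that the gap may rarely or never arise. Major surgery needs a written perioperative treatment plan (protocol 6.6). Protocol Table 12 records completion of cover only at the visit on SDay 2 to 14 or on SDay 28, and the window also runs through antithrombotic treatment. All this suggests that cover after major surgery usually lasts past SDay 3, where the two windows coincide. Anticipated or planned surgery is an exclusion criterion (E 17), and non-urgent major surgery is to be postponed until after the trial. The floor may be there because a minor procedure may have no supplemental treatment to define its end, though the SAP does not say so. Protocol 6.6 also builds the plan for patients on fitusiran on the principles of bleed management, so treating a post-operative bleed could fall within the plan. The treatment-policy analyses and the reported counts of intercurrent events give a partial check.

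Most of this stands, and it limits the frequency and size of the problem. It does not supply the missing minimum, and the open question about the perioperative plan means that the same bleed could be classified in two ways.

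A reader might go further and infer that the shortfall is likelier on fitusiran, so that the ABR ratio is biased upward. The documents do not support that. Protocol Table 6 limits dose size and repeat intervals and sets no length of perioperative cover. Where those doses are insufficient, protocol 6.6 raises AT replacement, which would bring a separate and longer exclusion.

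**Conclusion.** The asymmetry is explicit in the operative primary rule, and no other section removes it. If cover for a major procedure ends before about SDay 3, its exclusion is 1 to 3 calendar days shorter than that of a minor procedure with the same cover. A treated bleed that starts in the gap and is handled outside the perioperative plan then counts in the on-treatment ABR. Each one in the efficacy period moves the cohort fitusiran rate by about 1% to 2%.

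That size rests on the planning ABR of 4 and full 162-day follow-up. Surgery counts and cover lengths are not in the documents. Because the exclusion applies in both periods, the direction of any net bias is unknown. A reader might also conclude that the plan in general keeps surgical bleeds after major surgery and removes them after minor surgery; that is true only when cover is short. This is a minor drafting inconsistency, worth correcting because it sits in the primary analysis. It concerns the analysis window only, not perioperative care.

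**What to change.** Replace the two surgery bullets in SAP 2.1.3.1 with one rule: for any surgery, major or minor, exclude from the day of the procedure until the last day of supplemental hemostatic or antithrombotic treatment under the perioperative plan, or until 72 hours after the procedure ends if that comes later. State in the SAP how this window relates to the open-ended exclusion in protocol 8.2.5.1, since even a 72-hour minimum is narrower than that text. It would also help to say whether factor or BPA given for a post-operative bleed counts as treatment under the plan.

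The cost is one sentence and one programming condition. The minor-surgery rule already needs the end time of surgery. Each major surgery loses at most 3 more days of follow-up (3/162 = 1.9% of that patient's efficacy period), and none when cover lasts to SDay 3 or beyond.
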